### **BOR and DCR**

BOR and DCR will be summarized by cohort for both phases and for phase I also overall.

### **DOR**

For DOR, the summary statistics (median,  $Q_1$  and  $Q_3$ ) will be based on the Kaplan-Meier analysis as described in Section 9.3.2. The number of patients with the event and the number of patients censored will be presented. The data for all patients will be displayed by the “swimmers plot” (sorted from the longest to the shortest duration), that will denote dose cohort for phase I, type of response (CR/PR/SD/PD) and ongoing response vs progression.

### **PFS and OS**

These endpoints will be analyzed as per the general methodology regarding the time-to-event analysis described in Section 9.3.2. The Kaplan-Meier estimate of the survival function will be displayed for all patients in phase I and by cohort in phase II. The summary statistics (median,  $Q_1$  and  $Q_3$ ) based on the Kaplan-Meier analysis will be determined, along with 95% confidence intervals. The number of patients with the event and the number of patients censored will be presented.

### **Waterfall graph**

These plots will display the best percentage change from baseline in the sum of the diameters of target lesions for each patient with measurable disease at baseline, sorted from the largest growth. The graph for phase I data will denote dose cohort. In addition, information on genetic mutations may be included (e.g. by color), see Section 9.11.

The listings of efficacy data will include

- All tumor measurements and responses
- All derived endpoints (BOR, DOR, PFS, OS)

## 9.7. Exposure

### 9.7.1. Study Treatment

#### **Duration of treatment exposure**

The duration of treatment exposure is defined as

$$\text{Treatment end date} - \text{Treatment start date} + 1.$$

It includes periods of interruptions. The duration of treatment exposure (in weeks) will be summarized by descriptive statistics by cohort. For each cycle, the number and percentage of patients who started that cycle will also be presented.

#### **Cumulative dose**

Cumulative dose is defined as the total dose taken during the treatment exposure and will be summarized by descriptive statistics by cohort.

#### **Dose intensity**

Dose intensity is defined as Cumulative dose/Duration of treatment exposure.

#### **Relative dose intensity**

Planned dose intensity is the dose by unit of time planned to be given to the patients as per the assigned cohort. Relative dose intensity is defined as Dose intensity/Planned dose intensity.

Cumulative dose, dose intensity and relative dose intensity will be summarized by descriptive statistics by cohort, with respect to an individual duration of treatment exposure as well as by cycle. The relative dose intensity will be summarized as continuous variable as well as by categories (<80%, 80%-120%, >120%).

#### **Dose reductions and interruptions**

The number and percentage of patients who had dose interruptions and modifications will be summarized by cohort, with the associated reasons.

The data on AK-01 administration will be listed, together with the above exposure characteristics.

### **9.7.2. Concomitant Medications**

Concomitant medications will be coded using the WHO Drug dictionary and summarized by ATC class III and preferred term. Only concomitant medications used during the treatment will be summarized and subjects with more than one recorded concomitant medication of particular ATC class and PT are counted only once for that ATC class and PT. All concomitant medication will be listed with reason for use, dose, route, and date of administration at a minimum, and time of administration if available.

## **9.8. Analyses of Safety**

Unless specified otherwise, all safety analyses will be performed in the FAS. Only safety assessments collected no later than 30 days after the Treatment end date will be summarized in tables. All safety assessments entered in the eCRF

(scheduled and unscheduled) will be listed and the assessments that did not occur within this timeframe will be flagged.

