not be reported as SAEs, however if an AE occurs during hospitalization for preplanned surgery that meets the above criteria, it will be reported as an SAE. SAEs due to progressive disease (including death) should not be reported as SAEs unless the investigator also deems there is a possible contribution of the IMP.

All SAEs occurring from the time the patient signs the ICD until the 30-day Follow-up visit must be reported to the sponsor or its designee regardless of relatedness to IMP or protocol procedures. Thereafter, SAEs will be reported only if the investigator feels the events were related to the IMP or a protocol procedure. Any SAEs after ICD signature and prior to administration of IMP will be reported if the investigator feels the events were related to a protocol procedure.

Appendix 1 outlines specific safety assessments for the 30-day Follow-up visit. All drug-related AE and SAEs will be followed until the events resolve, the events are no longer considered to be drug-related, the patient dies or is lost to follow-up, or until a new treatment is initiated for the patient. Frequency of follow-up evaluation is left to the discretion of the investigator.

The medical representative of the sponsor will monitor safety data throughout the course of the study. The sponsor and/or its designee will review SAEs within appropriate timeframes to meet reporting obligations imposed by regulatory authorities. All serious and unexpected AEs for this study will be reported to regulatory authorities in accordance with local laws, directives and regulations.

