- v. Patients will attend a follow-up visit 30 days (+/- 7 days) following the last dose of IMP.
- w. Patient survival will be confirmed approximately every 3 months for up to 1 year.

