## 7.3. General Definitions

**Treatment start date** is defined as the first date when a nonzero dose of AK-01 was administered. It will be derived based on the “AK-01 compliance” eCRF page.

**Treatment end date** is defined as the last date when a nonzero dose of AK-01 was administered. It will be taken from the field “Date of last drug intake” in the “Discontinuation from study treatment” eCRF page.

**Study day** for all assessments will be derived from the Treatment start date. It will be calculated as follows:

- Date of assessment – Treatment start date + 1; for assessments on or after Treatment start date
- Date of assessment – Treatment start date; for assessments before Treatment start date

**Last contact date** will be derived as the latest date of the following:

- Date of any visit
- Date of any other assessment, i.e. date of ECG, ECOG assessment, physical examination or pregnancy test, Date of blood sampling (laboratory tests, molecular profile, PK), date of skin/tumor biopsy, Date of last drug intake, date of discontinuation, start/end date regarding AK-01 compliance, AEs or concomitant medications, date of assessment regarding the response evaluation
- Date of last known alive in the Survival eCRF page

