### 9.8.2. Adverse Events

Detailed definitions and classification of AEs are specified in the Protocol, Section 6.5.3. All AEs will be coded using the MedDRA version 20.0 terminology and graded using NCI CTCAE v. 4.03.

A treatment-emergent AE is an AE that started or worsened (i.e. increased in severity) from the Treatment start date to 30 days after the Treatment end date. Only treatment-emergent AEs will be summarized in the tables. All AEs entered in the eCRF will be listed and AEs not considered as treatment-emergent will be flagged.

The data will be presented by cohort, see Section 7.6 regarding an assignment of particular AEs to the cohorts.

The number and frequency of patients reporting each treatment-emergent AE will be summarized by primary System Organ Class (SOC) and Preferred Term (PT), where subjects with more than one AE within a particular SOC and PT are counted only once for that SOC and PT.

To assess the relationship of the AE to administration of AK-01, the following terminologies are defined by the protocol: probably related, possibly related, unlikely, not related. For tables summarizing AEs related to AK-01, the options probably related and possibly related will be considered.

The following AE summaries will be presented (sorted alphabetically unless specified otherwise):

- Treatment-emergent adverse events, by SOC and PT
- Treatment-emergent adverse events in Cycle 1, by SOC and PT
- Treatment-emergent adverse events related to AK-01, by SOC and PT
- Treatment-emergent adverse events, by PT (sorted by overall decreasing frequency)
- Treatment-emergent adverse events in Cycle 1, by PT (sorted by overall decreasing frequency)
- Treatment-emergent adverse events related to AK-01, by PT (sorted by decreasing frequency)
- Treatment-emergent adverse events, by PT and maximum CTCAE grade (sorted by overall decreasing frequency)
- Treatment-emergent adverse events related to AK-01, by PT and maximum CTCAE grade (sorted by overall decreasing frequency)

- Treatment-emergent adverse events leading to dose reductions or interruptions, by SOC and PT
- Treatment-emergent adverse events related to AK-01 leading to dose reductions or interruptions, by SOC and PT
- Discontinuations due to adverse event, by SOC and PT
  - These events will be identified as AEs that have “Action taken with study drug” reported as “Drug withdrawn” AND at the same time, in the “Discontinuation page”, the reported reason is “Unacceptable toxicity”.

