### 9.8.3. Laboratory Data

All laboratory data will be converted to standard units and classified into CTC grades according to the NCI CTCAE v4.03.

Shift tables using CTC grades to compare baseline value to the worst post-baseline value will be produced for hematology and biochemistry laboratory parameters with CTC grades. Scheduled as well as unscheduled assessments will be considered.

The serum chemistry and hematology data will also be displayed graphically for phase II – for each parameter, mean  $\pm$  SE will be plotted by visit.

The listings for serum chemistry, hematology and urinalysis data will include all results, investigator’s assessment of clinical significance and abnormal values will be flagged.

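### The SAP's 30-day limit on tabulated safety assessments cuts through the protocol's 23-to-37-day window for the 30-day Follow-up visit, so compliant visits on days 31 to 37 are listed but not tabulated

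*SAP*

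**What the plan says.** SAP 9.8 sets one time limit for safety tables: "Only safety assessments collected no later than 30 days after the Treatment end date will be summarized in tables". Everything entered in the eCRF is still listed, and "the assessments that did not occur within this timeframe will be flagged". SAP 7.3 fixes the starting point: the Treatment end date "is defined as the last date when a nonzero dose of AK-01 was administered".

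Protocol Appendix 1 (headed Phase II), footnote v, sets the visit: "Patients will attend a follow-up visit 30 days (+/- 7 days) following the last dose of IMP". This is a planned safety visit. Protocol 6.5.4 says "Appendix 1 outlines specific safety assessments for the 30-day Follow-up visit", and the schedule marks physical exam, vital signs, ECOG status, hematology, clinical chemistry, concomitant medication and AE monitoring. ECG and urinalysis are not marked.

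The tables that would use these results are in SAP 9.8.3 ("Shift tables using CTC grades to compare baseline value to the worst post-baseline value will be produced") and SAP 9.8.4 (categories of potential clinical concern for blood pressure and pulse). For adverse events, SAP 9.8.2 counts onset or worsening up to 30 days after the Treatment end date, and "Only treatment-emergent AEs will be summarized in the tables".

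**The concern.** The SAP limit is a fixed day, while the visit it has to accommodate has a tolerance of a week on either side. Two patients who both comply with the protocol, one seen on day 30 and one on day 31, are treated differently: the first patient's results enter the tables and the second's do not. Only the appointment date separates them.

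Elsewhere the SAP allows for visit tolerances. In SAP 6.1 the confirmatory-scan rule subtracts the 5-day tolerance from 4 weeks to reach 23 days, and the PFS rule adds the assessment window to two 9-week intervals to reach 19 weeks. The safety limit makes no such allowance, and no other SAP text exempts the Follow-up visit.

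At stake is the completeness of the post-treatment laboratory and vital-sign summaries. Protocol 1.3 and 3.3.1 name neutropenia and thrombocytopenia as potential adverse events, and the hematology shift tables are where their laboratory grades are summarized.

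**Working it through.** **Inputs**

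- Table limit: day 30 after the Treatment end date, inclusive (SAP 9.8).
- Visit window: day 30 with a tolerance of 7 days (Protocol Appendix 1, footnote v).
- Starting point: the last dose for both (SAP 7.3; footnote v), so no conversion between clocks is needed.
- Distribution of actual visit days: not given in either document, so assumed below.

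**Step 1. Permitted days.** First day 30 − 7 = 23; last day 30 + 7 = 37. Number of days = 37 − 23 + 1 = 15.

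**Step 2. Permitted days beyond the limit.** Days 31 to 37: 37 − 30 = 7. Share of the window = 7/15 = 46.7%. Days 23 to 30, 8 of 15, are within the limit.

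**Step 3. From days to visits.** The 46.7% counts calendar days. It becomes a share of visits only under an assumption about timing.

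- Uniform over the window: 7/15 = 46.7%.
- Normal around day 30 with standard deviation s, restricted to the window, with whole days taken as unit intervals: share = [Φ(7.5/s) − Φ(0.5/s)] / [Φ(7.5/s) − Φ(−7.5/s)].

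| Assumed timing | Share of visits after day 30 |
|---|---|
| Normal, s = 1 day | 30.9% |
| Normal, s = 2 days | 40.1% |
| Normal, s = 4 days | 44.7% |
| Uniform, days 23 to 37 | 46.7% |

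For s = 1 the ratio is (1 − 0.6915)/1 = 0.3085. Visits centred before day 30 would lower these shares, and visits centred after it would raise them. Protocol 4.2.1 lets the follow-up assessments be brought forward before a new anti-cancer treatment, which pushes the shares down.

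**Step 4. Which outputs change.**

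- Affected: laboratory shift tables (SAP 9.8.3) and blood pressure and pulse categories (SAP 9.8.4).
- Not affected through this visit: ECG and urinalysis (not scheduled), and ECOG status (listed only, SAP 9.8.5).
- Not excluded by the sentence: the Phase II mean plots of laboratory values by visit (SAP 9.8.3), because the limit speaks of tables only. Read literally, plots and shift tables could rest on different data.

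**Step 5. Effect of moving the limit.** At day 30, 7 of the 15 permitted days are excluded; at day 33, 4; at day 37, none. A limit tied to the in-window visit also excludes none.

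**The case against.** The strongest defence is that the 30 days is a deliberate and consistent choice. The same period governs safety assessments (SAP 9.8), treatment-emergent events and on-treatment deaths (9.8.2) and incomplete event dates (7.7.2). A fixed period applies one rule to every patient, and no data are discarded. That is a good argument for the adverse event definition. It does not explain why results scheduled by the protocol and obtained within their own window should be left out of the tables.

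Several stronger readings are tempting but go beyond the documents.

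- *The data disappear.* They do not. SAP 9.8 lists and flags them; the omission is from tables only.
- *About half of all follow-up visits are lost.* That needs uniform timing, which nothing in the documents establishes.
- *Adverse events found at a late visit drop out.* SAP 9.8.2 selects by date of onset or worsening. An event that began by day 30 and was recorded on day 35 is still tabulated. What falls outside is an event that starts or worsens on days 31 to 37. Protocol 6.5.3 restricts AE reporting after the last dose to ongoing or related events. For SAEs, Protocol 6.5.4 is wider: "All SAEs occurring from the time the patient signs the ICD until the 30-day Follow-up visit must be reported". An SAE with onset on day 34, before a day-36 visit, is thus collected and listed but absent from the SAE tables. This is a real but narrow remainder. Lengthening the period to 37 days is a trade-off: for a patient seen on day 23 it would count days on which unrelated SAEs are no longer collected.
- *The shift tables will miss late cytopenias.* They could, but only if a patient's worst grade first appears on days 31 to 37. Hematology and chemistry are also taken during treatment and at the Discontinuation visit, and unscheduled samples count. Nothing in the documents suggests that a first worst grade so late is common.

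**Conclusion.** The mismatch is explicit and needs no assumption: 7 of the 15 compliant visit days fall after the table limit. Planned hematology, chemistry and vital signs from those visits are left out of the shift tables and vital-sign categories because of scheduling alone. The share of visits affected, about 31% to 47%, rests on assumed timing between tightly centred on day 30 and uniform. It refers to one visit per patient. It is not the share of patients whose tabulated worst grade would change; that share cannot be derived from the documents and is probably much smaller.

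Severity is minor to moderate. The primary endpoints, Cycle 1 DLTs in Phase I and ORR in Phase II, are unaffected. The documents do not support calling the 30-day treatment-emergent period an error.

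**What to change.** In SAP 9.8, tabulate safety assessments collected up to the later of two dates: 30 days after the Treatment end date, or the date of the 30-day Follow-up visit if it is held within its 7-day tolerance. Apply the same limit to the flag in the listings. SAP 7.7.3 handles incomplete laboratory dates by the rule in 7.7.2, which uses 30 days, so say there that laboratory dates follow the new limit.

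Leave the treatment-emergent definition in 9.8.2 and the event-date rule in 7.7.2 as they are.

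The cost is SAP wording before database lock and one date limit in the programs; no new visits, samples or patients are needed. The downside is small: laboratory and vital-sign tables would hold some data up to day 37 while the treatment-emergent period ends at day 30, and the limit would vary between patients from day 30 to day 37. A footnote on the affected tables covers both.

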### 9.8.1. Phase I Primary Objective

The number and frequency of patients experiencing a DLT at the end of Cycle 1 will be presented by cohort and overall. A listing of DLTs will be provided. All patients evaluable for DLT assessment (see Section 8.1 for the definition) will be considered.

### 9.8.2. Adverse Events

Detailed definitions and classification of AEs are specified in the Protocol, Section 6.5.3. All AEs will be coded using the MedDRA version 20.0 terminology and graded using NCI CTCAE v. 4.03.

A treatment-emergent AE is an AE that started or worsened (i.e. increased in severity) from the Treatment start date to 30 days after the Treatment end date. Only treatment-emergent AEs will be summarized in the tables. All AEs entered in the eCRF will be listed and AEs not considered as treatment-emergent will be flagged.

The data will be presented by cohort, see Section 7.6 regarding an assignment of particular AEs to the cohorts.

The number and frequency of patients reporting each treatment-emergent AE will be summarized by primary System Organ Class (SOC) and Preferred Term (PT), where subjects with more than one AE within a particular SOC and PT are counted only once for that SOC and PT.

To assess the relationship of the AE to administration of AK-01, the following terminologies are defined by the protocol: probably related, possibly related, unlikely, not related. For tables summarizing AEs related to AK-01, the options probably related and possibly related will be considered.

The following AE summaries will be presented (sorted alphabetically unless specified otherwise):

- Treatment-emergent adverse events, by SOC and PT
- Treatment-emergent adverse events in Cycle 1, by SOC and PT
- Treatment-emergent adverse events related to AK-01, by SOC and PT
- Treatment-emergent adverse events, by PT (sorted by overall decreasing frequency)
- Treatment-emergent adverse events in Cycle 1, by PT (sorted by overall decreasing frequency)
- Treatment-emergent adverse events related to AK-01, by PT (sorted by decreasing frequency)
- Treatment-emergent adverse events, by PT and maximum CTCAE grade (sorted by overall decreasing frequency)
- Treatment-emergent adverse events related to AK-01, by PT and maximum CTCAE grade (sorted by overall decreasing frequency)

- Treatment-emergent adverse events leading to dose reductions or interruptions, by SOC and PT
- Treatment-emergent adverse events related to AK-01 leading to dose reductions or interruptions, by SOC and PT
- Discontinuations due to adverse event, by SOC and PT
  - These events will be identified as AEs that have “Action taken with study drug” reported as “Drug withdrawn” AND at the same time, in the “Discontinuation page”, the reported reason is “Unacceptable toxicity”.
- Discontinuations due to adverse event related to AK-01, by SOC and PT
- Treatment-emergent serious adverse events, by SOC and PT
- Treatment-emergent serious adverse events related to AK-01, by SOC and PT
- Dose-limiting toxicities, by SOC and PT (phase I only)
- DLT-equivalent toxicities, by SOC and PT

Deaths will be summarized by reason (AE/disease progression/other), and those caused by an AE by SOC and PT. Three types of tables will be prepared:

- On-treatment deaths (i.e. all deaths occurring up to 30 days after the Treatment end date)
- On-treatment deaths related to AK-01
- All deaths

An overall summary of AEs will be presented and will include frequency and percentage of patients with:

- Any treatment-emergent adverse event
- Any treatment-emergent adverse event in Cycle 1
- Any dose-limiting toxicities
- Any treatment-emergent adverse event related to AK-01
- Any treatment-emergent adverse event leading to dose reductions or interruptions
- Discontinuations Due to Adverse Event
- Any treatment-emergent serious adverse event
- On treatment deaths due to adverse event
- On treatment deaths due to adverse event related to AK-01

The following AE listings will be presented:

- Adverse events
- Dose-limiting toxicities

- Serious adverse events
- Adverse events leading to dose reductions or interruptions
- Adverse events leading to discontinuation (listing the same events as in the table “Discontinuations due to adverse event”).
- Deaths

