### 3.3.2. Dose Modifications for Toxicity

Dose modifications are permitted as described below for toxicities that emerge throughout the study.

IMP may be withheld for up to 21 days to allow sufficient time for recovery from toxicity, but patients who do not recover within this period will be withdrawn. Following recovery, IMP may be resumed at the same dose or at a reduced dosing frequency, depending on the type and severity of toxicity experienced (see [Table 1](#)).

[Table 1](#) describes AK-01 dose modifications for patients who experience toxicity.

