## 4.2. Discontinuation

### 4.2.1. Discontinuation of Patients

In accordance with the guidelines of the International Conference on Harmonisation (ICH) Good Clinical Practices (GCP), Health Canada, European Medicines Agency, and United States Food and Drug Administration, a patient may withdraw their participation in this study at any time.

Criteria to discontinue patients from study treatment will include but will not be limited to:

- Objective disease progression based on RECIST v. 1.1 as determined by the investigator
- Unacceptable toxicity
- Significant protocol violation
- Global deterioration of health status
- Lost to follow-up
- Refusal of further treatment by patient
- Study termination by sponsor
- Dosing is delayed by more than 21 days due to toxicity

Reasons for discontinuation from the study may include:

- Study termination by sponsor
- Lost to follow-up
- Withdrawal of consent

If a patient is found to not meet the enrollment criteria but was inadvertently enrolled, the patient must be discontinued from the study and the sponsor or its designee must be informed. An exception to this requirement may be granted in rare circumstances where the patient has a serious or life threatening condition for which there is no effective alternative therapy and, in the opinion of the investigator, is receiving benefit from study treatment. In this case, the investigator must obtain documented approval from the sponsor's medical representative to allow the patient to continue receiving IMP.

Following discontinuation or withdrawal, the investigator will request that the patient return all unused IMP and packaging, and participate in the Discontinuation and 30-Day Follow-up visits. If it is in the best interest of the patient to start a new anti-cancer treatment prior to this date, the follow-up assessments may be performed sooner, so long as they are completed prior to initiation of the new therapy.

The primary reason for withdrawal, patient outcome, and the date of withdrawal will be documented. Every effort will be made to adequately follow the patient for any unresolved AEs. In the case of withdrawal due to global deterioration of health status, the signs, symptoms, or results that motivated this decision will be documented.

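### The SAP rule for AE discontinuations accepts only the reason unacceptable toxicity, so it may leave out patients stopped because a toxicity delay exceeded 21 days

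*SAP*

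**What the plan says.** SAP 9.8.2 plans a table of discontinuations due to AE by SOC and PT and states how its events are found. The rule opens with "These events will be identified as AEs that have" and sets two conditions: the action taken with study drug must be *Drug withdrawn*, and the Discontinuation page must carry one particular reason, namely *Unacceptable toxicity*. Both conditions must hold. The same section plans three related outputs:

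- a version of the table restricted to AEs related to AK-01;
- a line for discontinuations due to AE in the overall AE summary;
- a listing of AEs leading to discontinuation, which is defined as showing the same events as the table.

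No separate rule is given for the first two.

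Protocol 4.2.1 introduces its list with "Criteria to discontinue patients from study treatment will include but will not be limited to". Two bullets concern toxicity. One is "Unacceptable toxicity", the same words that the SAP uses for the reason. The other is "Dosing is delayed by more than 21 days due to toxicity". Protocol 3.3.2 shows how a patient reaches the second: drug may be withheld for up to 21 days to allow recovery, "but patients who do not recover within this period will be withdrawn".

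**The concern.** A patient whose toxicity does not resolve within the permitted interruption, and who is therefore taken off drug, has stopped because of an adverse event. A reader of the clinical study report would expect to find that patient in a table titled discontinuations due to AE. Under the SAP rule, inclusion depends on which of two toxicity reasons was recorded, and nothing in the SAP maps one reason to the other.

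The route matters for this drug. Protocol 1.3 names bone marrow toxicity, including neutropenia and thrombocytopenia, among the potential AEs identified from Phase I. Table 1 in Protocol 3.3.2 handles hematologic toxicity by withholding drug until counts recover. Prolonged cytopenia is therefore a plausible way to reach the delay criterion.

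Tolerability is a secondary objective in both phases. If the gap is real, it works in one direction only: the discontinuation table would understate toxicity-related stopping. The listing could not reveal the omission because it is tied to the same events. The report could also show a disposition table and an AE-discontinuation table whose toxicity counts disagree without explanation.

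**Working it through.** The plan gives no figure to reproduce, so the check is one of logic, followed by a statement of scale.

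**Step 1. The rule.** Let A be that the AE action is *Drug withdrawn*, and B that the Discontinuation page reason is *Unacceptable toxicity*. SAP 9.8.2 counts the AE only if A and B are both true.

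**Step 2. Apply it to the two toxicity bullets in Protocol 4.2.1, assuming each is a selectable reason.**

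| AE action | Recorded reason | A | B | Counted? |
|---|---|---|---|---|
| Drug withdrawn | Unacceptable toxicity | true | true | yes |
| Drug withdrawn | Toxicity delay over 21 days | true | false | no |

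The second row is the gap.

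**Step 3. Is a separate option on the form likely?** The form itself (eCRF version 1.3, cited in SAP section 1) is not available. Two indications favour it. The reason in the SAP rule matches a Protocol 4.2.1 bullet word for word. SAP 7.3 names an eCRF page for discontinuation from study treatment, which is the subject of that protocol list. Neither indication is proof.

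**Step 4. Which outputs are affected?**

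- AE-discontinuation table: affected, because the rule is stated there.
- Listing of AEs leading to discontinuation: affected, because it is defined by the table's events.
- Related-AE table and overall summary line: affected if they use the same rule, since no other is given.
- Treatment disposition summary (SAP 9.4): not affected. It reports stopping by reason, but carries no AE term.
- General AE tables and the full AE listing (SAP 9.8.2), and dose interruptions with reasons (SAP 9.7.1): not affected by this rule.

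**Step 5. Scale.** With k missed patients in a cohort of n treated patients, the reported rate falls short by k/n. The documents do not give k, so a range is assumed for illustration. The cohort maximum of 30 is from Protocol 3.2, and 15 is a cohort size used in Protocol 3.6.

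| k (assumed) | n = 30 | n = 15 |
|---|---|---|
| 0 | 0 points | 0 points |
| 1 | 1/30 = 3.3 points | 1/15 = 6.7 points |
| 2 | 2/30 = 6.7 points | 2/15 = 13.3 points |
| 3 | 3/30 = 10.0 points | 3/15 = 20.0 points |

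Only the loss per patient follows from the documents. Nothing in them says which row applies.

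**The case against.** The strongest objection is that the rule works on eCRF fields and the eCRF cannot be seen. The Protocol 4.2.1 list is open-ended and is a list of stopping criteria, not a coding list. Its bullets are not said to be mutually exclusive, and failure to recover within 21 days can fairly be called unacceptable toxicity. Table 1 contains other toxicity withdrawals, such as Grade 4 non-hematologic events and recurrence at the reduced frequency, that have no bullet of their own, so bullets and form reasons need not correspond one to one. If sites record delay patients as unacceptable toxicity, nobody is missed. This stands, and it is why the point is conditional. It does not remove the need for clarification, because the SAP does not say how such patients are coded.

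A reader might infer that the table certainly undercounts, or that a particular true rate can be set against the planned one. The documents support neither: the form is unseen and no count is given.

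A reader might also infer that these patients vanish from the report. They do not. Disposition shows them by reason, and their AEs remain in the general outputs. What would be lost is the link between stopping and a specific SOC and PT.

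On importance, discontinuation due to AE is not a named endpoint. SAP 6.3 lists type, frequency and severity of AEs, and laboratory parameters. The table drives no test or dose decision. That also stands.

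Finally, the second condition probably has a purpose: it stops an AE marked *Drug withdrawn* from being counted when the patient's recorded primary reason was progression or refusal. That is a good reason to keep a two-part rule, but not a reason to limit it to one of two toxicity reasons.

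**Conclusion.** The point holds in conditional form. As written, the SAP rule recognises one toxicity reason where Protocol 4.2.1 lists two. If the Discontinuation page offers both, patients stopped under the delay criterion are left out of the AE-discontinuation table and its listing, and probably out of the related-AE table and the overall summary line. The error can run only towards undercounting, by 3.3 points per missed patient in a full cohort of 30. The number missed may be zero.

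Two assumptions carry this conclusion: that the page mirrors the protocol list, and that the AE responsible is recorded as *Drug withdrawn*. If it were left recorded as an interruption, the first condition would fail whatever reason was chosen. The primary endpoint is untouched. This is a definition worth correcting because the correction is cheap and leaves the cross-check in place.

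**What to change.** Keep the two-part rule in SAP 9.8.2 and widen its second condition, so that the Discontinuation page reason may be either *Unacceptable toxicity* or the toxicity delay of more than 21 days. State that the same rule governs the AE-discontinuation table, the related-AE table, the overall summary line and the listing. Check the option list on eCRF version 1.3 first. If the page has no separate delay option, a sentence saying how these patients are recorded settles the matter.

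Dropping the second condition and relying on *Drug withdrawn* alone is not recommended, because it would lose the check against the recorded primary reason.

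The cost is one line of SAP text and of programming, and a reported rate that may be slightly less favourable. Only an analysis definition changes; the clinical stopping criteria stay as they are.
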